10.2.1.5. Amount of Opioid Medication Used

At each study visit, study personnel will record the amount of opioid medication that the patient reports having taken over the previous 24 hours. Each type of medication and whether it was used because of OM pain or other types of pain will be noted in the eCRF. Each opioid dose will be converted to an "oral morphine dose equivalent dose" and the total amount of opioid used for each patient summed over each visit from baseline to 6 weeks post-completion of the radiation therapy. Patients with missing visits will have their opioid usage estimate for the missing data by using an average of their opioid use for the available visits using formula detailed in the SAP. The mean and median amount of total opioids used in each of the treatment groups will be compared.

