10.2.2.4. Assessment of Pain

At each study visit, the patient's assessment of their pain over the previous 24 hours will be recorded by study personnel using a scale of 1-10. Patients with missing visits will have their pain estimated for the missing data by averaging their pain scores reported using the formula detailed in the SAP.

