12.5. Selection of Primary Analysis Population

Given that OM does not occur at a significant rate in patients that have not received at least 55 Gy of cumulative radiation, the primary analysis population will be limited to those patients that have received at least 55 Gy of radiation. Only those patients that receive sufficient radiation therapy are at risk of developing the disease (i.e., SOM). Should SGX942 reduce the most severe cases of OM prior to reaching 55 Gy of radiation such that there is a reduced dropout rate from anticancer therapy, the worst cases of OM in the placebo group, but not the SGX942 group, will be eliminated from the analyses. Thus, if bias is introduced, it is likely to lead to a conclusion that SGX942 is less efficacious than it actually is.

The primary efficacy analysis will be based on this mITT population that is defined as all randomized subjects receiving a minimum of 55 Gy of cumulative radiation analyzed per treatment groups defined by their randomization treatment assignment.

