## 9.4.9 Amount of Opioid Medication Used

At each study visit, study personnel will record the amount of opioid medication that the patient reports having taken over the previous 24 hours. Type and usage of medication will also be collected. Descriptive statistics of the amount of opioid medication used, normalized to a calculated oral morphine equivalent, will be summarized by visit. Total opioid used will be summarized though the treatment period (baseline through 6 weeks post-radiation treatment) and compared between treatment groups. Values will be compared between treatment groups using a one-way ANOVA test. Mean  $\pm$  standard deviation will be plotted for each visit.

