## 5. ANALYSIS ADJUSTMENTS DUE TO IMPACT OF COVID-19 PANDEMIC

Reference is made to the FDA Guidance for Industry, "Statistical Considerations for Clinical Trials During the COVID-19 Public Health Emergency," June 2020. While many of the patients were in the treatment portion of their participation, the COVID-19 pandemic interrupted normal clinical operations with an impact on patient retention, the number and degree of protocol deviations, the ability to obtain protocol specified measurements, the ability to ship clinical specimens, and decreased the availability of clinical research personnel to perform protocol related activities. The ultimate impact of this unprecedented disruption in the clinical trial and the resulting number of dropouts, missing data, and partial data remains unclear at this time, Currently, the protocol specifies a last-value forward method of handling missing data and all patients in the mITT population are included in the analyses even if the final 4-6 weeks of experimental therapy is not delivered. To address the impact of the pandemic on this study, we will:

- Drop patients at specific sites in which the COVID-19 activities created extensive problems with documentation, data collection and/or patient enrollment and compliance;
- Terminate the trial early; and

•	Conduct sensitivity analyses on primary, secondary and safety analyses to understand the
	potential impact of the pandemic (with an assigned "start date" to the pandemic of January 1,
	2020 based on the onset of disease potentially impacting participating European sites).

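### Missing opioid and pain visits take the patient's own flat average, which understates opioid totals when data stop soon after 55 Gy, and the SAP lacks the promised formula.

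*Protocol*

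**What the plan says.** Protocol 10.2.1.5 has staff "record the amount of opioid medication that the patient reports having taken over the previous 24 hours" at each visit. The endpoint is "the total amount of opioid used for each patient summed over each visit from baseline to 6 weeks post-completion of the radiation therapy". A missing visit is estimated "by using an average of their opioid use for the available visits using formula detailed in the SAP". For pain, Protocol 10.2.2.4 states: "Patients with missing visits will have their pain estimated for the missing data by averaging their pain scores reported". It too refers to a formula in the SAP.

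The SAP gives no such formula. SAP 9.4.9 says "Total opioid used will be summarized though the treatment period (baseline through 6 weeks post-radiation treatment) and compared between treatment groups", by one-way ANOVA, with no rule for missing visits. SAP 9.4.8 compares pain visit by visit with a Wilcoxon test and defines no cumulative score, although SAP 2.2.2 and 9.3.2 list cumulative pain as an endpoint. SAP Appendix 1, item 4 covers missing data for SOM duration only. Item 5 says that "the protocol specifies a last-value forward method of handling missing data", without naming an endpoint.

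Total opioid use is the fifth and last step of the fixed sequence and is analysed in mITT (SAP 2.2.1, 9.3.1). That population requires at least 55 Gy (SAP 3.2.3).

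**The concern.** A patient's own mean is a reasonable stand-in for a missing visit only if the profile is roughly flat. Here it is not expected to be. Current mucositis is an exclusion criterion (Protocol 7.2), the oral lesions develop under radiotherapy, and recovery falls within the six weeks afterwards. If data stop during the rise or early peak, the average is pulled down by the low-use early weeks and applied to later visits where use may be high. The imputed total then reflects how long the patient was observed as well as how much opioid was used.

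Two things are at stake. One is bias in a formally tested secondary endpoint. The other is that the derivation is left open, because averaging, last-value-forward and no imputation give quite different totals. Missing data are a live issue in this trial: SAP section 2 expects them to increase during the pandemic, and Appendix 1, item 5 keeps mITT patients in the analyses even when the last 4-6 weeks of study drug were not delivered.

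**Working it through.** The documents give no figure for opioid totals, attrition or imputation, so there is none to reproduce. The opioid curves and leaving rates below are assumptions.

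**Calendar (Protocol Table 7, 7-week RT).** Baseline 1 + twice weekly for 9 weeks 18 + weekly visits at post-RT weeks 3-6 4 = 23 records (22 if the conditional week-5 visit is not held). Fractions to 55 Gy: 55/2.2 = 25 to 55/2.0 = 27.5, so 28. At five per week that is week 5.0 to 5.6. A patient leaving at the end of week 5 has 1 + 2×5 = 11 records.

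**Formula.** With n visits seen, observed sum S and N = 23, averaging gives S + (N − n)·S/n = N·S/n.

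**One assumed curve.** No use to week 2, linear rise to a peak of 1 at week 5, plateau to week 9, falling to 0.25 at week 13. True sum over 23 visits = 13.8.

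| Leaves at week | n | S | N·S/n | Imputed/true |
|---|---|---|---|---|
| 5 | 11 | 3.3 | 6.9 | 0.50 |
| 6 | 13 | 5.3 | 9.4 | 0.68 |
| 7 | 15 | 7.3 | 11.2 | 0.81 |
| 8 | 17 | 9.3 | 12.6 | 0.91 |
| 9 | 19 | 11.3 | 13.7 | 0.99 |

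Missing only the four visits of weeks 1-2 gives 23×13.8/19 = 16.7, a ratio of 1.21, so the bias reverses.

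**Grid of 672 assumed curves.** Onset week 1-4, peak week 4-7, plateau end week 7-10, level at week 13 of 0-75% of peak, baseline level 0-40% of peak. Median imputed/true total:

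| Leaves at week | Averaging (range) | Share of curves too low | Last value forward | No imputation |
|---|---|---|---|---|
| 5 | 0.63 (0.08-0.98) | 100% | 1.00 | 0.30 |
| 6 | 0.75 (0.25-1.05) | 99% | 1.06 | 0.43 |
| 7 | 0.86 (0.46-1.10) | 95% | 1.09 | 0.56 |
| 8 | 0.93 (0.66-1.12) | 84% | 1.09 | 0.69 |
| 9 | 0.99 (0.81-1.11) | 59% | 1.07 | 0.82 |

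**A leaver in SOM.** Assume dose D at each visit in SOM, none otherwise, first use on day 36, data stopping on day 43. Then 14 visits are seen, 3 of them at D, and 9 are missing. Averaging gives 23×3/14 = 4.9D. Last-value-forward gives 3 + 9 = 12D. With exponential SOM at the plan's medians, the expected true total is 3D + D·Σexp(−ln2·(t − 43)/median) over the remaining visit days (46, 50, 53, 57, 60, 67, 74, 81, 88). This is 6.7D at a median of 13 days and 5.5D at 8 days. Averaging is 26% or 11% low, and last-value-forward is 79% or 118% high. For a day-46 leaver averaging is 16% or 2% low, and for day 50 it is 12% or 0% low.

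**Arm contrast.** 200,000 simulated patients per arm, SOM onset normal (mean day 38, SD 5), exponential duration with medians 13 and 8 days, opioid use only in SOM, leaving only while in SOM after day 36. At 2%, 3% and 5% per visit the runs shrank the true difference by 5-6%, 8-9% and 12-14%.

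**The case against.** Several objections have force.

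- Protocol 7.3 lets withdrawn patients complete whatever assessments they permit, other than OM scoring. Opioid and pain history can therefore continue, and leaving does not always mean missing data. This stands, and it limits the number of patients affected.
- mITT removes patients who leave before 55 Gy, where the bias would be greatest. This also stands. What remains is leaving from about week 5 onwards.
- A reader might take Protocol 12.5 ("OM does not occur at a significant rate in patients that have not received at least 55 Gy") as showing that visits before 55 Gy are pain-free. It does not. The sentence justifies the choice of population, the same section allows for severe cases before 55 Gy, and opioids are recorded for other pain as well. If need starts at week 2, only 5 of the 11 records at week 5 precede it. The understatement at weeks 5-7 does not depend on that reading, because the grid includes onset from week 1.
- A reader might infer that the leaver's total is 69-85% too low, since each imputed visit is 0.15D to 0.31D for leaving on days 39 to 50. That is a per-visit error while use stays at D and ignores recovery. The error in the whole total for leavers on days 43-50 is about 0-26%.
- A reader might infer that the SAP prescribes last-value-forward for opioids. Appendix 1, item 5 names no endpoint, and item 4 just before it carries forward WHO scores. The sentence may refer only to those.
- The endpoint is last in the sequence and is formally tested only if the preceding steps succeed. This limits the consequence.

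**Conclusion.** The concern holds in a limited form. Followed as written, the averaging rule understates the opioid total for mITT patients whose data stop in roughly weeks 5-7. The bias fades or reverses for leaving at weeks 8-9 and for missed early visits. The SAP does not supply the formula to which the protocol defers, so the operative rule is undefined.

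At arm level the effect is modest: a contrast roughly 5-14% too small under the assumed leaving rates, towards the null. This gives no ground for inferring a false efficacy claim. Nor do the documents support a statement that placebo will have more leavers after 55 Gy, because the remark on differential dropout in Protocol 12.5 concerns the period before it. Attrition, its difference between arms, the opioid curves and the extent of data after withdrawal are all assumed here. The direction for early leavers is well supported; the size is not known.

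For pain, the point rests on the protocol rule and the listed cumulative endpoint, since SAP 9.4.8 plans only visit-wise tests.

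**What to change.** Before unblinding:

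1. In Protocol 10.2.1.5 and 10.2.2.4, replace the average over available visits with a time-matched rule.
2. Write that rule into SAP 9.4.9, and into 9.4.8 for the cumulative pain endpoint. The SAP has no averaging rule to delete; the text has to be added.
3. Use any opioid and pain data collected after withdrawal. Between two attended visits, interpolate. After the last available visit, use multiple imputation from the patient's recent values and other patients' values in the same study week.
4. Make last-value-forward a sensitivity analysis only, because it tends to overstate the total when recovery is not observed.
5. State which endpoints the last-value-forward sentence in SAP Appendix 1, item 5 covers.

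The cost is protocol and SAP wording and a small amount of programming. No new data are needed. The downside is a slightly more complex derivation.

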10.2.2 Other Secondary Analyses

In addition to the primary secondary analyses performed in hierarchical order, several additional secondary analyses will be performed.

10.2.2.1. Cumulative Number of Treatment Breaks

For the analysis purposes for this study, treatment breaks will be defined as missing 3 or more scheduled consecutive RT treatment sessions. The cumulative duration of treatment breaks for each patient will be calculated by summing the actual number of treatment break days (≥3 days per break) through the final RT treatment and comparing these between treatment groups.

10.2.2.2. **Duration of SOM in the ITT Population**

Using the above definitions, the duration of SOM will be compared between treatment groups in all patients randomized (ITT population).

10.2.2.3. Duration of Ulcerative Oral Mucositis (UOM)

UOM is defined as a WHO score ≥ 2 . Resolution of UOM is defined as the first assessment with a WHO score ≤ 2 with no further reports of a WHO grade of ≥ 2 . The duration of UOM is defined as the number of days from the first WHO score ≥ 2 to the first day with WHO score ≤ 2 with no further occurrence of WHO score ≥ 2 . If the patient has not met the requirements for resolution of

Original: 11 January 2017 Confidential Page 49 of 67

UOM by the 6-week post-RT visit, he/she will be considered censored at that visit (or point of discontinuation of the study, if the patient discontinues prior to that timepoint). For statistical reasons, patients who do not experience SOM will be treated as having a duration of UOM of 0.01. The analysis will be done in the mITT population.

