6.2.1 Oral Mucositis (OM) Grading

OM will be evaluated by personnel trained in the use of the WHO Oral Mucositis Grading system which includes both physical and functional information. This grading system is widely utilized in OM clinical research trials including the Phase 2 trial and is shown in Table 8.

Score	Findings		
0	No findings OR Pain or erythema (not both)		
1	Pain and erythema AND No ulcer		
2	Ulcer and/or pseudomembrane, AND Able to eat solid food AND Able to drink		
3	Ulcer and/or pseudomembrane, AND Not able to eat solid food AND Able to drink		
4	Ulcer and/or pseudomembrane, AND Not able to eat solid food AND Not able to drink		

Table 8: WHO Oral Mucositis Grading System

Only medical personnel at the site who have undergone training and certification in using the WHO Grading system will perform the OM assessments.

6.2.2 **Tumor Status**

The tumor response to treatment will be used as a safety endpoint. Results at 12 weeks and 12 months post-RT will be compared to the Screening results using the RECIST 1.1 system. The evaluation criteria for the target lesion (the primary head and neck carcinoma) are shown in Table 9; the criteria for non-target lesions are shown in Table 10; and the criteria for overall categorization of the tumor status are shown in Table 11. In addition, details pertaining to recurrence of disease, additional therapy, or surgery required after the active treatment phase of the trial is completed will be collected and recorded in the eCRF throughout all follow up visits until 12 months following the last RT treatment.

Confidential

Original: 11 January 2017 Amendment 1: 29 November 2017

Amendment 2: 22 January 2018 Amendment 3: 17 September 2019

Table 9: RECIST Evaluation of the Target Lesion

Target Lesion Response	Measurement	
Complete Response (CR)	All target lesions gone	
Partial Response (PR)	>30% decrease from baseline	
Progressive Disease	>20% increase from smallest sum of longest diameter recorded since treatment started (best response)	
Stable Disease (SD)	Neither Progressive Disease nor Partial Response	

Table 10: RECIST Evaluation of the Non-target Lesion

Target Lesion Response	Measurement	
Complete Response (CR)	All non-target lesions gone Tumor markers gone	
Stable Disease (SD)	Persistence of ≥1 non-target lesion Tumor marker level elevated	
Progressive Disease	Enlargement of non-target lesions	

Table 11: Overall RECIST Response

Target Lesions	Non-target Lesions	New Lesions	Overall Response

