10. ASSESSMENT OF EFFICACY

10.1. Primary Efficacy Endpoint

Clinical evaluation of mucositis will be performed and graded by trained study evaluators in accordance with WHO Oral Mucositis Grading system, as detailed in Table 8 at each study drug administration visit and once a week through 6 weeks post-RT.

The duration of SOM is the primary endpoint for this clinical trial.

SOM is defined a WHO score of ≥ 3 (3 or 4). Resolution of SOM is defined as the first assessment with a WHO score ≤ 3 with no further reports of a WHO grade of ≥ 3 . The duration of SOM is defined as the number of days from the first WHO score ≥ 3 to the first day with WHO score ≤ 3 with no further occurrence of WHO score ≥ 3 . If the patient has not met the requirements for resolution of SOM by the 6-week post-RT visit, he/she will be considered censored at that visit (or point of discontinuation of the study, if the patient discontinues prior to that timepoint). To facilitate calculation of a log-rank test without censoring patients with desirable outcomes (no SOM), patients who do not experience SOM will be treated as having a duration of SOM of 0.01 days. The primary endpoint analysis will be conducted in the mITT population.

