## INTRODUCTION

This statistical analysis plan (SAP) provides a more technical and detailed elaboration of the statistical analyses of efficacy and safety as outlined and/or specified in the study protocol. Specifications of tables, figures, and data listings are contained in a separate document (table shells).

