#### 9.4.3 **Duration of UOM**

UOM is defined as a WHO score  $\geq$ 2. The duration of UOM is defined as the number of days from the first WHO score  $\geq$ 2 to the first day with WHO score  $\leq$ 2 with no further occurrence of WHO score  $\geq$ 2. A log-rank test will be used to compare the duration of UOM between the two treatment groups.

Resolution of UOM is defined as the first assessment with a WHO score <2 with no further reports of a WHO grade of  $\ge 2$ . If the patient has not met the requirements for resolution of UOM by the 6-week post-RT visit, he/she will be considered censored at that visit (or the point of discontinuation from the study, if the patient discontinues prior to that time point). For statistical reasons, patients who do not experience UOM will be treated as having a duration of 0.01 days.

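### Protocol 10.2.2.3 gives 0.01 days of UOM to patients without SOM, so it discards the ulcer duration of every patient whose worst grade is 2; SAP 9.4.3 states the coherent rule

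*Protocol*

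**What the plan says.** Protocol 10.2.2.3 defines the condition and its duration by grade 2: "UOM is defined as a WHO score ≥ 2" and "The duration of UOM is defined as the number of days from the first WHO score ≥ 2". It also censors unresolved cases at the 6-week post-RT visit or at discontinuation. It then adds, for statistical reasons, that "patients who do not experience SOM will be treated as having a duration of UOM of 0.01". No unit is given.

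SAP 9.4.3 covers the same endpoint with the same definition and censoring, but its rule reads "patients who do not experience UOM will be treated as having a duration of 0.01 days". It specifies a log-rank test.

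Protocol 10.1 has the parallel rule for the primary endpoint: "patients who do not experience SOM will be treated as having a duration of SOM of 0.01 days". There the trigger fits the endpoint. Protocol 10.1 defines SOM as WHO 3 or 4. The WHO table in Protocol 6.2.1 describes grade 2 as "Ulcer and/or pseudomembrane, AND Able to eat solid food AND Able to drink", which is ulcerative but not severe.

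Protocol 10.2.2 and SAP 2.2.2 and 9.3.2 list UOM duration among the other secondary endpoints, outside the fixed sequence of five.

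**The concern.** The value 0.01 stands for a patient who never had the condition. Under the protocol sentence it also goes to patients who had ulcers, possibly for weeks, and never reached grade 3. Their observed duration is discarded and replaced by the best possible outcome. The number of patients affected in each arm depends on how many stop at grade 2, so a difference between arms in SOM incidence enters the UOM comparison even if ulcers last equally long. If incidence is equal, a real effect on ulcer duration is harder to see.

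The two documents also leave two prespecified rules for one listed endpoint. Unless this is settled before unblinding, the choice could be made, or appear to be made, with the data in view.

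**Working it through.** **Step 1: the rules side by side.**

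| Worst WHO grade | UOM? | SOM? | Protocol 10.2.2.3 | SAP 9.4.3 |
|---|---|---|---|---|
| 0 or 1 | no | no | 0.01 | 0.01 |
| 2 | yes | no | 0.01 | observed or censored duration |
| 3 or 4 | yes | yes | observed or censored duration | observed or censored duration |

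The rules differ only for worst grade 2, and there they differ for every patient. Example with illustrative days: grade 2 from day 21, resolved at the visit on day 49, never grade 3. The SAP gives 49 − 21 = 28 days; the protocol gives 0.01. This step does not depend on the inequality signs in the resolution text, which may be misread from the PDF.

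**Step 2: how many patients.** The documents give no absolute incidence of SOM or UOM, so this is assumption. With UOM in 95% and SOM in 60% to 80%, the recoded share is 95 − 80 = 15% to 95 − 60 = 35%. At 70% SOM it is 25%.

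**Step 3: effect on the test.** Assumed inputs: 115 mITT patients per arm (of 130 planned), UOM in 95% of each arm, exponential ulcer duration with median 35 days, onset uniform over days 14 to 35, visits every 3.5 days, and follow-up to 6 weeks after 7 weeks of RT (day 49 + 42 = 91). Both 0.01 rules were applied to each simulated trial, with a two-sided 5% log-rank test.

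| SOM incidence, placebo v SGX942 | Resolution hazard ratio | Rejects, protocol rule | Rejects, SAP rule |
|---|---|---|---|
| equal | 1 | about 5% | about 5% |
| 70% v 65% | 1 | about 8% | about 5% |
| 70% v 60% | 1 | about 14% | about 5% |
| 70% v 50% | 1 | about 47% | about 5% |
| 70% v 70% | 1.5 | about 48% | about 73% |
| 70% v 60% | 1.5 | about 78% | about 73% |

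Repeat runs gave 14% to 16% in the third row and 47% to 50% in the fourth.

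**Step 4: check by hand, 70% v 60%, no effect on duration.**
- At 0.01 days the protocol rule produces 0.30 × 115 = 34.5 events on placebo and 0.40 × 115 = 46 on SGX942, 80.5 in all. Expected on SGX942 is 40.25, so O − E = 5.75.
- The variance there is 80.5 × 0.25 × 149.5/229 = 13.1.
- Later events have mean O − E of zero. Mean follow-up after onset is 91 − 24.5 = 66.5 days, so about 1 − 0.5^(66.5/35) = 73% of the remaining 149.5 patients resolve, or about 109. With 69/149.5 = 46% of them on SGX942, they add about 109 × 0.46 × 0.54 ≈ 27 to the variance.
- The expected z is 5.75/√40 ≈ 0.91, so P(Z > 1.96 − 0.91) ≈ 15%, in line with the simulation.
- Under the SAP rule both arms have 0.05 × 115 = 5.75 events at 0.01 days, so O − E is zero and rejection stays near 5%.

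**The case against.** The case for leaving this alone has real weight.

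- **The SAP already has the coherent rule.** Protocol 12.1 refers to the SAP for complete analysis details. The SAP is also the later document: it cites a guidance of June 2020, while the last protocol amendment is dated 17 September 2019. A statistician programming from SAP 9.4.3 would not make the error. This stands, and it lowers the practical risk. It is not a precedence clause, however. The SAP describes itself as elaborating "statistical analyses of efficacy and safety as outlined and/or specified in the study protocol", and 9.4.3 does not acknowledge any departure from the protocol.
- **It is a slip, not a chosen analysis.** This is probably right. The sentence closely follows 10.1, and the definitions around it contradict it. It is still the current protocol text.
- **The endpoint is low in the plan.** This stands. A rejection here is a nominal p-value outside the confirmatory sequence.
- **The large figures need large differences in incidence.** This also stands. Going from 70% to 50% is a 20/70 = 29% relative reduction. The Phase 2 relative reductions at this dose (Protocol 4.5) were 7% overall, 18% with every-third-week cisplatin and 22% in HPV-negative patients. From an assumed 70%, a 7% reduction gives 65%, where rejection is about 8%. An 18% reduction gives about 57%, where a separate simulation with other inputs (95 per arm, 90% UOM, median 28 days) gave about 17%.

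A reader might infer that the UOM test becomes largely a repeat of SOM incidence. The working does not support that: at 60% to 80% SOM incidence most patients keep their observed duration, and the test retains about 48% power for a pure duration effect. Partly is the right word.

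**Conclusion.** The inconsistency is certain from the text alone. Protocol 10.2.2.3 contradicts its own definition of UOM and SAP 9.4.3, and a literal reading gives a wrong value for every patient whose worst grade is 2.

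The size of the effect rests on assumed incidences and durations. Following the protocol rule would be harmless for false rejection when SOM incidence is equal, modest at small differences, and serious only at large ones. Power falls from about 73% to 48% if the drug shortens ulcers without changing SOM incidence. There is no loss if SOM incidence also falls from 70% to 60%.

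A reader might also infer that the trial's main conclusions are at risk. They are not: the primary analysis, the UOM AUC, SOM incidence and the rest of the ordered sequence are calculated separately. Nor do the documents show that the protocol rule would actually be programmed. The point is a correction worth making before unblinding, not a defect in the confirmatory analysis.

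**What to change.** In the 0.01 sentence of Protocol 10.2.2.3, replace SOM with UOM and add the unit, days, so that it matches SAP 9.4.3. No extra sentence on grade-2-only patients is needed, because the duration and censoring rules in that section already cover them once the trigger is right.

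The cost is one word and a unit, by amendment or clarification memo. No new data are needed and no other analysis changes.
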